7.3 Subject Population(s) for Analysis

All populations.

CONFIDENTIAL

8 Safety and Adverse Events

8.1 Definitions

Adverse Event

An **adverse event** (AE) is any symptom, sign, illness or experience that develops or worsens in severity during the course of the study. Intercurrent illnesses or injuries will be regarded as adverse events. Abnormal results of diagnostic procedures are considered to be adverse events if the abnormality:

- results in study withdrawal
- is associated with a serious adverse event
- is associated with clinical signs or symptoms
- leads to additional treatment or to further diagnostic tests
- is considered by the investigator to be of clinical significance

Serious Adverse Event

Adverse events are classified as serious or non-serious. A **serious adverse event (SAE)** is any AE that is:

- fatal
- life-threatening
- requires or prolongs hospital stay
- results in persistent or significant disability or incapacity
- a congenital anomaly or birth defect
- an important medical event

Important medical events are those that may not be immediately life threatening, but are clearly of major clinical significance. They may jeopardize the subject, and may require intervention to prevent one of the other serious outcomes noted above. For example, drug overdose or abuse, a seizure that did not result in in-patient hospitalization, or intensive treatment of bronchospasm in an emergency department would typically be considered serious.

All adverse events that do not meet any of the criteria for serious should be regarded as **non-serious adverse events**.

Adverse Event Reporting Period

The study period during which adverse events must be reported is normally defined as the period from the initiation of any study procedures to the end of the study treatment follow-up. For this study, the study treatment follow-up is defined as 30 days following the last administration of study treatment.

Preexisting Condition

A preexisting condition is one that is present at the start of the study. A preexisting condition will be recorded as an adverse event if the frequency, intensity, or the character of the condition worsens during the study period.

General Physical Examination Findings

CONFIDENTIAL

At screening, any clinically significant abnormality will be recorded as a preexisting condition. At the end of the study, any new clinically significant findings/abnormalities that meet the definition of an adverse event must also be recorded and documented as an adverse event.

Post-study Adverse Event

All unresolved adverse events will be followed by the investigator until the events are resolved, the subject is lost to follow-up, or the adverse event is otherwise explained. At the last scheduled visit, the investigator will instruct each subject to report any subsequent event(s) that the subject, or the subject's personal physician, believes might reasonably be related to participation in this study.

Abnormal Laboratory Values

A clinical laboratory abnormality should be documented as an adverse event if any one of the following conditions is met:

- The laboratory abnormality is not otherwise refuted by a repeat test to confirm the abnormality
- The abnormality suggests a disease and/or organ toxicity
- The abnormality is of a degree that requires active management; e.g. change of dose, discontinuation of the drug, more frequent follow-up assessments, further diagnostic investigation, etc.

Hospitalization, Prolonged Hospitalization or Surgery

Any adverse event that results in hospitalization lasting >24 hours or prolonged hospitalization should be documented and reported as a **serious adverse event** unless specifically instructed otherwise in this protocol. Any condition responsible for surgery will be documented as an adverse event if the condition meets the criteria for and adverse event.

Neither the condition, hospitalization, prolonged hospitalization, nor surgery are reported as an adverse event in the following circumstances:

- Hospitalization or prolonged hospitalization for diagnostic or elective surgical procedures for a preexisting condition. Surgery should **not** be reported as an outcome of an adverse event if the purpose of the surgery was elective or diagnostic and the outcome was uneventful.
- Hospitalization or prolonged hospitalization required to allow efficacy measurement for the study.
- Hospitalization or prolonged hospitalization for therapy of the target disease of the study, unless it is a worsening or increase in frequency of hospital admissions as judged by the clinical investigator.

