3.1 General Design

Adolescents will receive 16 weeks of continuation treatment. They will be treated by the same clinicians who provided their acute phase treatment. The personalized continuation treatment plan is illustrated below.

Continuation IPT-A. The goal of IPT-A²⁰ is to decrease depressive symptoms by focusing on current interpersonal difficulties and helping the individual improve his or her relationships and interpersonal interactions. This is accomplished through review of the

[figure not shown]
[figure not shown]
adolescent's significant relationships which leads to the identification of the interpersonal problem areas on which to focus the treatment, development of communication and interpersonal problem solving skills, and role-playing. During the Continuation IPT-A sessions, the therapist will continue to emphasize the interpersonal strategies that were learned and practiced during the acute phase, and address any current interpersonal problems before they result in a recurrence of depressive symptoms. Adolescents who have responded to acute phase treatment (CGI-I = much improved or very much improved) will attend 4 biweekly IPT-A sessions followed by 2 monthly sessions. Adolescents who showed a partial response to acute phase treatment (CGI-I = minimally improved) will attend 8 weekly IPT-A sessions followed by 2 monthly sessions.

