8.2 Recording of Adverse Events

At each contact with the subject, the investigator must seek information on adverse events by specific questioning and, as appropriate, by examination. Information on all

CONFIDENTIAL

adverse events will be recorded immediately in the source document, and also in the appropriate adverse event module of the case report form (CRF). All clearly related signs, symptoms, and abnormal diagnostic procedures results will be recorded in the source document, though should be grouped under one diagnosis.

All adverse events occurring during the study period must be recorded. The clinical course of each event will be followed until resolution, stabilization, or until it has been determined that the study treatment or participation is not the cause. Any serious adverse event that occurs after the study period and is considered to be possibly related to the study treatment or study participation should be recorded and reported immediately.

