8.5.1 Internal Data and Safety Monitoring Board

The PI will maximize the safety and privacy of all study participants and ensure the integrity, validity, and confidentiality of data collection procedures through regular monitoring of clinical and research activities during weekly project meetings with the study staff. At the start of each treatment session, clinicians will be required to ask both adolescents and parents whether any adverse events or suicidality have occurred in the past week. Clinicians will report to the PI any serious or unexpected adverse events, unexpected problems that involve risk to the participants or others, and any breaches of confidentiality. The PI will report these to the Quorum within 24 hours of their occurrence. The PI will also submit an annual progress report to the IRB summarizing the data and safety monitoring activities and outlining 1) whether participants' safety, privacy and confidentiality has been consistently assured, 2) whether research instruments have been administered in a uniform manner and in a way that protects participants' privacy, 3) progress towards recruitment goals, quality of data collection (e.g., appropriate completion of forms), and participant retention/ attrition rates, and 4) a review of new scientific literature pertinent to the safety of participants or the ethics of research participation. The study psychiatrists, *the independent safety monitor*, psychologists, research clinicians, and clinical interviewers will take all appropriate actions to prevent and treat psychiatric emergencies in participating adolescents and family members as outlined in the Procedures to Minimize Potential Risks.

On an annual basis, the PI and [name] will monitor the safety, quality and conduct of this study and decide whether adequate subject safeguards are in place. They will review: 1) the progress of the proposed study, including assessments of data quality and participant recruitment, accrual and retention; 2) outcome and adverse event data to determine whether there is any change to the anticipated benefit-to-risk ratio of study

CONFIDENTIAL

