10.1 Study Monitoring Plan

This study will be monitored according to FDA/GCP guidelines. (Explain who will be monitoring what sites or self-monitoring according to the U of M plan. The investigator will allocate adequate time for such monitoring activities. The Investigator will also ensure that the monitor or other compliance or quality assurance reviewer is given access to all the above noted study-related documents and study related facilities (e.g. pharmacy, diagnostic laboratory, etc.), and has adequate space to conduct the monitoring visit.

The PI will maximize the safety and privacy of all study participants and ensure the integrity, validity, and confidentiality of data collection procedures through regular monitoring of clinical and research activities during weekly project meetings with the study staff. At the start of each treatment session, clinicians will be required to ask both adolescents and parents whether any adverse events or suicidality have occurred in the past week. Clinicians will report to the PI any serious or unexpected adverse events, unexpected problems that involve risk to the participants or others, and any breaches of confidentiality. The PI will report these to the Internal Review Board (IRB) at the University of Minnesota within 24 hours of their occurrence. The PI will also submit an annual progress report to the IRB summarizing the data and safety monitoring activities and outlining 1) whether participants' safety, privacy and confidentiality has been consistently assured, 2) whether research instruments have been administered in a

CONFIDENTIAL

uniform manner and in a way that protects participants' privacy, 3) progress towards recruitment goals, quality of data collection (e.g., appropriate completion of forms), and participant retention/ attrition rates, and 4) a review of new scientific literature pertinent to the safety of participants or the ethics of research participation. The study psychiatrists, *the independent safety monitor* psychologists, research clinicians, and clinical interviewers will take all appropriate actions to prevent and treat psychiatric emergencies in participating adolescents and family members as outlined in the Procedures to Minimize Potential Risks.

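### The required adverse-event question looks back one week, but sessions are up to four weeks apart and no contact is scheduled in the final 30 days of the reporting period.

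*Combined protocol and SAP*

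**What the plan says.** Section 8.1 sets the adverse-event reporting period as "the period from the initiation of any study procedures to the end of the study treatment follow-up", with that follow-up "defined as 30 days following the last administration of study treatment". Section 8.2 adds: "All adverse events occurring during the study period must be recorded". It also obliges the investigator to enquire about adverse events at every contact, and it names no recall period.

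The question itself is given in the monitoring sections. Section 10.1, in wording shared with section 8.5.1, reads "At the start of each treatment session, clinicians will be required to ask both adolescents and parents", and what they ask is "whether any adverse events or suicidality have occurred in the past week".

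On timing, section 3.1 says "Adolescents will receive 16 weeks of continuation treatment". Responders "will attend 4 biweekly IPT-A sessions followed by 2 monthly sessions"; partial responders "will attend 8 weekly IPT-A sessions followed by 2 monthly sessions". Those on fluoxetine also have medication visits: monthly for responders; every two weeks for two months and then monthly for partial responders already on it; weekly for four weeks and then every two weeks for partial responders who start it. Independent assessments are at study weeks 24 and 32, and nothing is scheduled later. After the last visit, section 8.1 relies on participants to report events that they or their physician think may be related to the study, and on follow-up of events still unresolved.

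**The concern.** A seven-day look-back leaves no gap when visits are weekly. It cannot span intervals of 14 or 28 days. A therapist who asks exactly what sections 8.5.1 and 10.1 require, and no more, will not enquire about part of the period that sections 8.1 and 8.2 treat as reportable.

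The gap is also uneven. Participants seen more often are asked about more of their time, and visit frequency depends on response status and on fluoxetine use. IPT-A-only responders are asked about the least, and they have no medication visits at which other safety forms are completed.

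What is at stake is the completeness of the adverse-event record. The annual review in sections 8.5.1 and 10.1 uses adverse-event data to judge whether the balance of benefit and risk has changed and whether the study should go on. After treatment, the stated duty covers all events, while the stated means of collection covers only those someone believes related.

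**Working it through.** **Inputs.** Treatment lasts 16 weeks (section 3.1), which is 16 × 7 = 112 days. Follow-up is 30 days (section 8.1). The whole period is 112 + 30 = 142 days, counting from the start of continuation treatment. The look-back is 7 days (sections 8.5.1 and 10.1). Visit schedules are from section 3.1.

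**The plan's own figure.** With a month taken as 4 weeks:
- Responders: 4 × 2 + 2 × 4 = 16 weeks.
- Partial responders: 8 × 1 + 2 × 4 = 16 weeks.

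Both reproduce the stated duration.

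**Assumptions.** Each session falls at the end of its interval, every session is attended, the last treatment is on day 112, and medication visits count as treatment sessions. The weekly-then-two-weekly medication schedule is read as applying to those starting fluoxetine. The plan does not say how medication visits line up with IPT-A sessions, so the low end of each range puts them in the same weeks as far as possible and the high end staggers them.

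**Continuation weeks with a session.**
- IPT-A, responders: 2, 4, 6, 8, 12, 16 (6 weeks).
- IPT-A, partial responders: 1 to 8, 12, 16 (10 weeks).
- Medication, responders on fluoxetine: 4, 8, 12, 16, or staggered 3, 7, 11, 15. Distinct weeks in all: 6 to 10.
- Medication, partial responders already on fluoxetine: 2, 4, 6, 8, 12, 16, or staggered 1, 3, 5, 7, 11, 15. Distinct weeks in all: 10 to 12.
- Medication, partial responders starting fluoxetine: 1 to 4, then 6, 8, 10, 12, 14, 16, or staggered 1 to 4, then 5, 7, 9, 11, 13, 15. Distinct weeks in all: 12 to 14.

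**Coverage.** Days covered = 7 × distinct weeks with a session.

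| Group | Days covered | Share of 112 treatment days | Share of 142 days not covered |
|---|---|---|---|
| Responders, IPT-A only | 42 | 37.5% | 70.4% |
| Responders on fluoxetine | 42 to 70 | 37.5% to 62.5% | 50.7% to 70.4% |
| Partial responders already on fluoxetine | 70 to 84 | 62.5% to 75.0% | 40.8% to 50.7% |
| Partial responders starting fluoxetine | 84 to 98 | 75.0% to 87.5% | 31.0% to 40.8% |

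For example, IPT-A-only responders: 42/112 = 37.5%, leaving 112 − 42 = 70 treatment days unasked, and (142 − 42)/142 = 70.4% of the whole period. Partial responders are covered on all 56 of the first 56 days.

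The assessments at study weeks 24 and 32 are continuation weeks 8 and 16. Both already hold an IPT-A session in this layout, so counting them would not change the table.

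**Final window.** 30/142 = 21.1% of the period has no scheduled contact after it begins, if treatment runs to week 32.

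**With a look-back to the last contact.** Coverage becomes 112/112 treatment days in every group, or 112/142 = 78.9% of the whole period. One contact at the end of the 30 days makes it 142/142.

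**The case against.** The strongest reply is that section 8.2 is the protocol's collection rule and already requires specific questioning at every contact without a recall limit. Nothing says that the past-week wording in the monitoring sections narrows it. A clinician who follows both would ask about the whole interval. This stands to the extent that events are not necessarily lost. It does not remove the mismatch: section 8.2 sets the investigator's duty without a time frame, and the only explicit question given to clinicians is shorter than their visit intervals.

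Other safety data are also collected. Therapists check suicidality at each session, and medication visits use the C-SSRS and Side Effects forms (section 8.4). The C-SSRS is among the assessment measures at weeks 24 and 32 (section 3.1). These offset the gap in part; how far cannot be said, because their recall windows are not stated.

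Four stronger readings are tempting, and the documents do not support them:

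- *Most of the reporting period goes unasked for everyone.* This is true of responders, borderline for partial responders already on fluoxetine, and false for those starting it. Every partial responder is on fluoxetine in continuation, so IPT-A sessions alone understate their contacts.
- *The primary safety endpoints are undercounted.* Section 3.4 measures them with the C-SSRS, the Side Effects Measure and vital signs, not with the past-week question.
- *A planned group comparison is biased.* Section 7.2 plans no comparison of adverse-event rates between groups, and the groups are non-randomised. Reporting events per person-week by group would not correct unequal questioning, so it is not recommended.
- *The last 30 days are empty.* Unresolved events are followed, related events may be self-reported, and families have a pager number (section 5.5). If treatment stops before week 32 and the family agrees to further evaluations (section 4.4.2), an evaluation may fall inside the window.

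**Conclusion.** The point holds as an inconsistency between what must be recorded and what clinicians are told to ask. Taken alone, the past-week question leaves 12.5% to 62.5% of treatment days unasked, depending on group and on how visits line up. The largest and only fixed figure is for responders on IPT-A only. Questioning under that wording is therefore incomplete and uneven by group. The shares rest on the stated schedule assumptions; missed sessions would lower coverage.

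Separately, for participants treated to week 32, the final 30 days depend on passive reporting of events believed related, which is narrower than the all-events duty. The documents do not show how many events, if any, would be missed. The point merits correction because safety ascertainment improves at almost no cost.

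**What to change.** 1. In sections 8.5.1 and 10.1, replace the past-week look-back with *since the last study contact*, and use the same wording for the section 8.2 enquiry at the week 24 and week 32 assessments. This closes the treatment-period gap in every group.
2. Reconcile the 30-day reporting period in section 8.1 with how events are collected after the last visit. Either schedule one brief contact at the end of the 30 days, or state that events in that window are passively reported.

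The first change is a phrase in two sections and on the session form. The second costs one sentence or, with 30 participants, at most about 30 short calls.

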8.4 Stopping Rules

Adolescents will enter continuation treatment at week 16. Assessments will be conducted at week 24 and 32. The adolescent completes the BDI-II at each therapy session, and therapists assess suicidality and change in adolescents' clinical status using the CGI-I and CGI-S at each therapy session. The subject will be evaluated by *an independent safety monitor* if at any time any of the following occur: 1) a suicide attempt, 2) serious suicidal ideation (with a plan and/or intent) and refusal to contract for safety, 3) psychiatric hospitalization, 4) possible need for psychiatric hospitalization, or 5) significant worsening of depressive or other clinical symptoms (CDRS-R > 76 or CGI improvement score > 5). Adolescents will be removed from the study immediately following review if the *independent safety monitor* deems that the patient requires treatment outside of study protocols or if the treatment provided in the study is contraindicated. In these cases, the family will be provided with referrals to receive treatment out of the protocol.

While fluoxetine is generally well tolerated, side effects can occur. Adverse events will be closely monitored during each psychopharmacological treatment visit using the C-SSRS and the Side Effects forms. The study psychiatrist will review with families the following potential fluoxetine related adverse events: gastrointestinal complaints (nausea, pain, diarrhea, and constipation), dizziness, allergic reactions, increased anxiety or irritability, increased activation/restlessness, sleep changes (increased or decreased), sexual side effects, appetite changes (increase or decrease), unusual thoughts, sweating, fatigue, suicidal ideation/attempts/and or behaviors. In addition to these issues, the study psychiatrist will make the adolescents and their families aware of the Food and Drug Administration advisory that the use of antidepressants like the SSRIs may lead to suicidal thinking/attempts in depressed youths and that the FDA has placed product warning label with information highlighting the need for close observation for worsening of depression and the emergence of suicidality in children treated with these medications. This information will be a part of the consent process for the study so that families are aware of these issues when considering participation in

CONFIDENTIAL

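### Section 8.1 lets a depression admission judged not to be a worsening fall outside SAE reporting, which does not fit section 4.4.1, and its 24-hour wording does not match the SAE definition

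*Combined protocol and SAP*

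**What the plan says.** Section 8.1 deals with hospitalisation in two places. The SAE list counts as serious any adverse event that "requires or prolongs hospital stay", with no minimum length. The later paragraph on hospitalisation says: "Any adverse event that results in hospitalization lasting >24 hours or prolonged hospitalization should be documented and reported as a" serious adverse event, unless the protocol instructs otherwise.

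That paragraph is followed by a list of exemptions, introduced by "Neither the condition, hospitalization, prolonged hospitalization, nor surgery are reported as an adverse event in the following circumstances". The third exemption is "Hospitalization or prolonged hospitalization for therapy of the target disease of the study, unless it is a worsening" or, as the second limb of the exception, admissions become more frequent. Whether the exception applies is left to the clinical investigator, and neither worsening nor increased frequency is given a criterion or a reference point.

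Other sections bear on the same event:
- Section 8.1 (Preexisting Condition) makes a preexisting condition an adverse event if it worsens during the study.
- Sections 4.4.1 and 8.4 send the participant to an independent safety monitor on any of several triggers, among them "3) psychiatric hospitalization, 4) possible need for psychiatric hospitalization". Section 4.4.1 places these triggers under a withdrawal reason that is itself a marked worsening of symptoms.
- Sections 8.3.1 and 8.3.2 set sponsor and IRB notification for SAEs, and section 8.5 bases medical monitoring on their number and type.

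**The concern.** The target-disease exemption is a poor fit for a depression study. The admissions it can remove are psychiatric ones, in adolescents some of whom start fluoxetine or have the dose raised during the study (section 5.2). Section 3.4 makes suicidality a primary safety endpoint, and section 8.4 cites the FDA advisory on antidepressants and suicidality in depressed youth.

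An SAE is by definition an adverse event that meets a seriousness criterion. An admission that is not an adverse event therefore cannot be an SAE, whatever its gravity. Whether a psychiatric admission enters the safety record as an SAE may then turn on which sentence of section 8.1 is applied, and on one person's judgement in an open-label study. With 30 participants, very few such events may occur, so each classification matters.

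**Working it through.** The check is a comparison of text; the plan gives no figure to reproduce.

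**Step 1: what the exemption does.** The lead-in covers both the condition and the admission. If the exemption applies, neither is reported as an adverse event, so neither can be an SAE.

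**Step 2: whether it can apply here.** Section 4.1 admits participants with CGI-I of 3 or better. Partial responders (CGI-I = 3) are only minimally improved and may still be symptomatic. An admission for persisting symptoms, with no clear deterioration, could be judged not to be a worsening. The second limb of the exception, an increase in frequency, might bring a first admission back into reporting, but the text does not say what frequency is compared with.

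**Step 3: the possible cases under section 8.1.**

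| Psychiatric admission | SAE list | Hospitalisation paragraph | Safety monitor (4.4.1, 8.4) |
|---|---|---|---|
| Over 24 hours, judged a worsening or more frequent | Serious | Report as SAE | Yes |
| 24 hours or less, judged a worsening or more frequent | Serious | Not addressed | Yes |
| Any length, judged neither | Not reached: not an adverse event | Exempt | Yes |

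The first row is consistent. The second is an unreconciled overlap. The third is the gap, and it conflicts with section 4.4.1, which associates the admission itself with worsening.

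**Step 4: what the third row misses.** Sponsor notification within 24 hours (8.3.1), IRB reporting of SAEs (8.3.2) and the SAE assessment in medical monitoring (8.5) all depend on SAE status. The safety monitor's task is to evaluate the participant and decide about removal; sections 4.4.1 and 8.4 assign no recording or classification of the event. Section 7.2 describes no tabulation of SAEs or admissions.

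**Step 5: scale.** Inputs: n = 30 (section 7.1) and, as an illustration, one omitted admission.
- Observed proportion with the event counted: 1/30 = 3.3%.
- With it omitted: 0/30 = 0%.
- Exact two-sided 95% upper limit for 0/30: 1 − 0.025^(1/30) = 11.6%.

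The documents give no expected admission rate, so these figures say how coarse a count in 30 is and nothing about how often the gap would be used.

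**The case against.** The strongest reply is that the exception does most of the work. Everyone enters at least minimally improved, section 8.1 makes worsening of a preexisting condition an adverse event, and section 4.4.1 itself links psychiatric admission to worsening. Read together, these would keep many depression admissions reportable. That stands. A reader might infer that the plan exempts depression admissions outright; it does not, because the sentence continues "unless it is a worsening or increase in frequency of hospital admissions as judged by the clinical investigator". A reader might equally infer that no admission in this population could be anything but a worsening. The documents do not support that either, and if it were true the exemption would remove nothing.

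Secondly, an exempt admission would still be seen. Besides the safety monitor, sections 8.5.1 and 10.1 require clinicians to ask about adverse events and suicidality at each treatment session and to tell the PI of unexpected problems involving risk, which are not confined to SAEs. Annual review covers outcome and adverse event data. This too stands: such an admission could be missing from the SAE record, but it would not go unnoticed. These routes do not make it an SAE or place it in an SAE count.

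Thirdly, the reference to "hospitalization lasting >24 hours" does not declare shorter stays non-serious, and the SAE list still covers them. This is correct, so the two passages are unreconciled rather than flatly contradictory.

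Finally, the suicidality endpoint is measured by the C-SSRS and does not depend on how an admission is classified. That is also right; what is at stake is the SAE record.

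**Conclusion.** The point holds in limited form. The target-disease exemption and section 4.4.1 need to be reconciled, and so do the two hospitalisation criteria within section 8.1. As written, a psychiatric admission judged neither a worsening nor an increase in frequency would be left out of SAE notification and SAE counts, and a stay of 24 hours or less could be handled inconsistently.

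The conclusion assumes that depression is the target disease and that an investigator could reasonably find an admission for persisting symptoms not to be a worsening. It does not assume that this would be common. The size cannot be estimated from the documents: one event is 3.3 percentage points of 30, and the 11.6% limit is for scale only. This is a matter of safety reporting. Sample size and the primary feasibility analysis are unaffected.

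**What to change.** In section 8.1, remove the target-disease exemption and the 24-hour qualifier for this study. State once that psychiatric hospitalisations are recorded and reported under the SAE list, and cross-refer to sections 4.4.1 and 8.4 so that the review trigger and the reporting rule describe the same event. Add to section 7.2 a simple tabulation of psychiatric hospitalisations: participants with at least one, and number of admissions.

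A cross-reference alone would be a smaller edit, but it would leave the judgement without criteria and the exempt route open. The cost of the fuller change is a few sentences of protocol wording and a slightly higher SAE count with its notifications. Treatment, dosing and withdrawal rules do not change.
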